
Study Design

This clinical study will involve 26 human subjects pre-screened at Columbia University with the presence of at least one implant presenting with early to moderate peri-implantitis. Peri-implantitis has been defined as an implant restoration with inflamed bleeding gingiva, probing depths around the implant of 5- 8mm, bone loss and exposure of threads around the implant (limited to one-third of the threads exposed). The purpose of this study is to determine the benefits of treating peri-implantitis with a closed laser approach known as the "Repair Protocol" using an Er,Cr:YSGG laser compared with traditional non-surgical therapy. Each subject, when determined to fall under the parameters of the study for peri-implantitis, will be randomly assigned to one of two groups: the test Er,Cr:YSGG laser group or the control group. The study will constitute a human double-blind randomized clinical trial in which both examiners and patients will be blinded to the treatment. In order to ensure the blinding of the patients, the laser will be applied to all implants, although it will not be activated in the control group. The therapist will be the same person throughout the study while the examiners will be calibrated. The two groups that will constitute the study and the procedures that will be applied are:

Experimental: Scaling and root planning with an ultrasonic or piezoelectric instrument and hand instrumentation with hand instruments. No prosthetic components will be removed. Application of laser therapy following the specifics of the company.

Control: Scaling and root planning with an ultrasonic or piezoelectric instrument and hand instrumentation with hand instruments. A sham, inactivated laser, treatment will be delivered.

Data to be collected include: Primary outcome measures will include: presence of bleeding on probing, probing depth, and the progression of bone loss around the implant, as measured with bone sounding under local anesthesia and radiographically with the aid of a stent. Secondary outcome measures will include: Gingival index (GI), Plaque Index, mobility, and suppuration.

Statistical Procedures

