Power calculation was done based on a study published by Lerario et al., 2016. To detect a difference of 1.72 mm (SD: 1.13mm) in probing depth at 9 months of follow-up after the use of Er,Cr: YSGG laser therapy we will need 13 patients in each of control and test groups (at 90% power, and alpha of 0.05). The ratio of sample size in group 1 to group 2 is 1.

Confidentiality

The study data will be recorded on paper during the appointments and will be transferred electronically to an encrypted computer designated for the study. The paper copy will only be seen and handled by the primary provider. When the data is transferred electronically, the hard copy will be destroyed. The excel files will only be located on encrypted laptops and desktops designated for the study. The data will be coded once it becomes electronic, and only the study team will have access to the identifiable data.

Limitations of compelled disclosure and mandatory reporting apply, and only during these special circumstances will the identities be disclosed.

Participants will only be seen by faculty and students participating in the study. During analysis of the data, patients will not be identified by name, only by a designated number identifying the patient in the health record software (coded). Only members of the study team will have access to the identifiable data.

Study Procedures

On the day of treatment, each subject will be randomly assigned to either the control group or the treatment group (envelopes with the respective groups will be prepared and drawn at the day of treatment). All ailing implants will be left closed with no incisions or flaps made to expose the implant surface surgically. Prior to treatment, radiographs will be taken utilizing a radiographic stent utilizing bite registration impression material, which will be stored for the final radiograph at the end of the study for standardization. In addition, gingival bleeding, recession, loss of attachment and tissue type will be recorded. All subjects receiving treatment will then be anesthetized with 2% lidocaine with 1:100,000 epinephrine, utilizing only buccal and palatal infiltrations with no interpapillary injections. The implant will be sounded with a periodontal probe to measure bone levels at four sites.

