In the control group, the implants will be debrided with curettes and ultrasonic scaler with standard tips. No prosthetic components will be removed in this study. The occlusion of the restorations supported by the ailing implant will be evaluated, and all balancing contacts, heavy occlusion, and excessive marginal ridge contacts will be removed.

In the Er,Cr:YSGG laser test group, the Er,Cr:YSGG laser will then be used to irradiate the implant surface utilizing a closed technique. The "Repair Protocol" will be utilized on the experimental implants. The "Repair Protocol" consists of several steps including but not limited to the following: Outer Pocket De-Epithelialization, Gingivectomy (as needed), De-Epithelialization and Retraction, Scaling and Root planing, Sulcular Debridement/Degranulation, Bone Decortication, Final Sulcular Debridement, and Compression with a wet 2X2. Occlusal adjustment will also be done at the conclusion of the procedure identical to the control group.

Oral hygiene instructions will be given to all patients after treatment.

Subjects will return for 1-week, 3-month, 6-month & 9-month evaluations. At the initial and the 9-month visits, the implant will be assessed for bleeding on probing, probing depths at four sites around the implant, clinical attachment level, and recession. Standardized radiographs will be taken at baseline and at the end of study at 9 months. At every recall visit, only supragingival polishing will be completed without the use of curettes or periodontal probes. At 9 months, the patient will receive a final evaluation for the study.

Medical Device

Device name: WaterLase iPlus

Device description: Er, Cr:YSGG laser

Device Model/Version #: WaterLase iPlus

Phase of Study: Feasibility

Manufacturer: Biolase Technology, Inc.

Recruitment

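### The plan does not say when the allocation envelope is opened relative to the shared debridement, and its two accounts of the test arm disagree on whether that debridement is the same in both arms.

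*Combined protocol and SAP*

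**What the plan says.** All references are to the combined protocol and SAP.

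- **Allocation.** Study Procedures states that "envelopes with the respective groups will be prepared and drawn at the day of treatment". It does not say who draws or opens the envelope, or at what point on that day.
- **Blinding.** Study Design states that "both examiners and patients will be blinded to the treatment". The therapist is not listed. The sham serves patient blinding: "the laser will be applied to all implants, although it will not be activated in the control group".
- **Operator.** "The therapist will be the same person throughout the study while the examiners will be calibrated" (Study Design).
- **Test arm, first account.** Study Design describes ultrasonic or piezoelectric scaling and hand instrumentation in the same words for both arms. The test arm then has "Application of laser therapy following the specifics of the company" and the control arm has the inactive laser.
- **Test arm, second account.** Study Procedures opens the Repair Protocol with outer pocket de-epithelialization and, as needed, gingivectomy. It continues with "De-Epithelialization and Retraction, Scaling and Root planing, Sulcular Debridement/Degranulation, Bone Decortication, Final Sulcular Debridement".
- **Control arm in Study Procedures.** "In the control group, the implants will be debrided with curettes and ultrasonic scaler with standard tips". No time, endpoint or checklist is given for this debridement.
- **Other shared care.** Occlusal adjustment has a listed set of contacts to remove. In the test arm it is done at the end of the procedure and declared identical to control. "Oral hygiene instructions will be given to all patients after treatment"; no provider or script is named.
- **Contrast.** Research Question(s)/Hypothesis(es) describes the second treatment as the laser on top of the traditional curette and ultrasonic approach.

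**The concern.** An add-on comparison isolates the laser only if the conventional part is delivered equally in both arms. Two features leave that unprotected.

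First, the person delivering the treatment is not blinded, and nothing withholds the allocation until the shared steps are finished. A therapist who knows the arm can, without intending to, debride more or less thoroughly. Debridement has no written endpoint, and no record of its delivery is planned. Blinded examiners and a sham laser guard against biased measurement and patient expectation. They do not equalise what is delivered.

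Second, the two accounts of the test arm define different comparisons. Under one, laser is added to the same debridement. Under the other, scaling follows pocket steps that the control arm does not receive, and the test arm has two further sulcular debridement steps. A difference at 9 months would then belong to the package and could not be credited to the laser alone.

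These are separate matters. The first is performance bias. The second concerns what the trial estimates, and a blinded operator would not change it.

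**Working it through.** **1. When must the therapist know the arm?**

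| | Study Design account | Study Procedures account |
|---|---|---|
| Steps before scaling, test arm | none listed | outer pocket de-epithelialization, gingivectomy as needed, de-epithelialization and retraction |
| Scaling and hand instrumentation | same wording in both arms | test: within the Repair Protocol; control: curettes and ultrasonic scaler |
| Steps after scaling, test arm | laser | sulcular debridement, bone decortication, final sulcular debridement, compression |
| Steps after scaling, control arm | sham | sham not mentioned |
| Latest point at which the arm is needed | after scaling | before scaling |
| Contrast delivered | laser added to the same debridement | whole Repair Protocol against conventional debridement |

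On the Study Design order the envelope could stay closed until debridement is complete, but nothing requires that. On the Study Procedures order it cannot, because steps given only in the test arm come first. On either order, test-arm occlusal adjustment and hygiene instruction, as now timed, follow the laser step.

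**2. The plan's own sample-size figure**

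Inputs (Statistical Procedures): difference 1.72 mm, SD 1.13 mm, power 90%, alpha 0.05, 13 per arm. Sidedness is not stated; two-sided is assumed.

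- Normal approximation: n = 2 × (1.960 + 1.282)² × (1.13/1.72)² = 9.07, so 10 per arm.
- Two-sample t-test: 10 per arm gives 89.6% power and 11 gives 92.4%, so 11 per arm.
- At 13 per arm, t-test power is 96.1%.

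The stated 13 is not reproduced; it is larger than its inputs require. An unstated dropout allowance would explain it: 11/(1 − 0.15) = 12.9, rounded up to 13. The present point does not depend on this, and the fix leaves the sample size unchanged.

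**3. Illustration of what an imbalance would do**

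The imbalances are assumptions; the documents give none. The SD of 1.13 mm is taken as common to both arms, with 13 analysed per arm.

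- SE of the difference = 1.13 × √(2/13) = 0.443 mm.
- Two-sided 5% t-test, 24 df, critical value 2.064; smallest significant difference = 2.064 × 0.443 = 0.91 mm.
- With no true laser effect, noncentrality = imbalance / 0.443.

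| Assumed imbalance | Noncentrality | Two-sided rejection | In favour of the better-treated arm | Share of 1.72 mm |
|---|---|---|---|---|
| 0 mm | 0 | 5.0% | 2.5% | 0% |
| 0.2 mm | 0.45 | 7.2% | 6.3% | 12% |
| 0.3 mm | 0.68 | 10.0% | 9.5% | 17% |
| 0.5 mm | 1.13 | 19.2% | 19.0% | 29% |

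The same percentages would follow from a bias of that size from any cause. The table shows sensitivity; it is not evidence that such a bias will occur.

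**The case against.** A reader might infer that the therapist certainly knows the arm before debriding. The documents do not say so. The draw is placed only on the day of treatment, and the Study Design order is compatible with opening after scaling. Knowledge before debridement follows only on the Study Procedures order.

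A reader might also infer that the therapist gives the hygiene instruction. No provider is named, and Confidentiality says that participating faculty and students see the participants.

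Several safeguards deserve credit. A single therapist removes differences between operators. Scaling is worded identically for both arms in Study Design. Occlusal adjustment has a written endpoint and an identity rule. Recall care is limited to supragingival polishing for everyone. It would also be too strong to say that imbalance could never be seen: Plaque Index is a secondary outcome and could reveal unequal home care, although the visit assessments in Study Procedures do not list it.

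It can fairly be added that scaling after the pocket has been treated is part of the test treatment, that the trial calls itself a pilot and its phase Feasibility, and that the illustrative imbalances have no source in the documents.

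All of this stands, and it limits the point. It does not supply an opening time, a debridement endpoint or a single account of the test arm. Plaque Index says nothing about how thoroughly the implant was debrided.

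**Conclusion.** The concern holds in limited form. The plan leaves the envelope opening unspecified relative to shared debridement, does not blind the one therapist, and gives two incompatible accounts of where scaling falls in the test arm. If Study Procedures governs, the arm is known before debridement and the trial compares the whole Repair Protocol with conventional debridement, which is not the add-on contrast in the research question.

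Knowledge of the arm at the laser step itself is unavoidable and is not a fault. The documents show neither that unequal debridement will occur nor in which direction, and its size cannot be estimated from them. The rise from 5% to about 7%, 10% or 19% rests on assumed imbalances of 0.2, 0.3 and 0.5 mm, a common SD of 1.13 mm and 13 analysed per arm. The case for acting rests on the low cost of the change and on the fact that unrecorded debridement cannot be reconstructed later. It is a recommended improvement, not a fatal flaw.

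**What to change.** 1. Reconcile Study Design and Study Procedures on the test-arm sequence, and align Research Question(s)/Hypothesis(es) with the result. Which sequence is clinically right is for the investigators.
2. State that the envelope is opened only after baseline measurements and after every shared step that the agreed sequence places before the first laser or sham step. On the Study Design order, that is after debridement is complete.
3. Give hygiene instruction from one fixed script before the envelope is opened, whoever delivers it.
4. If the Study Procedures order is kept, use the same written debridement endpoint in both arms, record instrumentation time per implant, report it by arm, and state the conclusion as the effect of the whole Repair Protocol.

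Occlusal adjustment should not be claimed as protected by this change. In the test arm it follows the laser, so later opening cannot help; its existing endpoint and identity rule remain its only safeguards.

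**Cost:** protocol wording, a later envelope opening on the same day and, under item 4, one extra form field. No added staff, visits or patients. Instrumentation time is only a partial measure of debridement effort, so item 4 makes an imbalance more visible but does not prevent it.

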
(Schwarz F, 2006) .Very few studies have been shown comparing the use of lasers as a means to sanitize the surface of the implant in comparison to other methods in a randomized, controlled environment. Previous studies verify that decontamination of the implant surface is very successful with the use of lasers, and this area of implant dentistry warrants further exploration. The aim of this study will be to explore the clinical effects of treating ailing implants non-surgically with the Er,Cr:YSGG laser, and compare the results to traditional methods of non-surgical therapy utilizing scalers and chlorhexidine rinses. This experiment will involve 26 human subjects pre-screened at Columbia University with the presence of peri-implantitis, which has been defined as an implant restoration with inflamed bleeding gingiva, bone loss and exposure of threads around the implant. This human clinical trial will utilize early to moderate peri-implantitis with no more than one third of threads exposed. The purpose of this study is to determine the benefits of treating peri-implantitis with a closed laser approach known as the "Repair Protocol" using an Er,Cr:YSGG laser compared with traditional non-surgical therapy. Each subject, when determined to fall under the parameters of the study for peri-implantitis, will be randomly assigned to one of two groups: the test Er,Cr:YSGG laser group or the control group. Primary outcome measures will be the presence of bleeding on probing, gingival index and the progression of bone loss around the implant, as measured with bone sounding under local anesthesia and radiographically with the aid of a standardized stent.

Lay Abstract

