The benefits of the study with enrolled patients is that they are able to receive treatment on ailing implants, whether through non-surgical means or with use of the laser. There is no compensation for the study, since it utilizes therapy that the patient would have needed regardless of participation. Currently, because no standardized protocol exists for the treatment of peri-implantitis, the benefit of this study will be to help collect data on treatment methods to gain additional knowledge on the most optimal treatment methods for peri-implantitis. This is an area that has very little conclusive evidence in terms of treatment modalities that are most effective, and more information is needed to determine the most effective way to treat peri-implantitis.

The alternative intervention for the subject is to not participate in the study and have the implant treated outside the study.

Data and Safety Monitoring

The data will be recorded on paper when the patient is seen by the operator. The study data will then be stored in an Excel file on an encrypted desktop or laptop computer immediately after the encounter with the patient. The paper documents used to collect data will then be destroyed once recorded electronically. There is minimal risk, and therefore there will be no data and safety monitoring board involved. The measurements will also be recorded in the electronic database for every patient (Axium) as a part of their dental treatment records.

The readings for gingival bleeding, periodontal probing, and attachment loss will be monitored for each patient at every visit and compared with previous readings for every patient. Monitoring for any unexpected outcomes, such as a severe increase in attachment loss/probing or gingival inflammation, will be completed after every visit with a patient for study purposes. Any patient showing aberrant findings and potential high risk for the study treatment will be identified and reported to the IRB. All investigators will be tasked with the data and safety monitoring for all patients.

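### Gingivectomy is named only for the laser arm, so lower probing depth could partly reflect a lowered margin; attachment level and recession are recorded but are in no outcome list

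*Combined protocol and SAP*

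**What the plan says.** **Treatment.** Study Procedures gives the steps of the laser arm's Repair Protocol, among them "Outer Pocket De-Epithelialization, Gingivectomy (as needed), De-Epithelialization and Retraction, Scaling and Root planing". For the other arm it says: "In the control group, the implants will be debrided with curettes and ultrasonic scaler with standard tips". Study Design adds a sham application of the inactivated laser. Gingivectomy appears nowhere else in the document. No criterion for it is given, and nothing requires its use or the amount of tissue removed to be recorded.

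**Measurement.** Before treatment: "In addition, gingival bleeding, recession, loss of attachment and tissue type will be recorded". At the initial and 9-month visits, "the implant will be assessed for bleeding on probing, probing depths at four sites around the implant, clinical attachment level, and recession". Data and Safety Monitoring adds: "The readings for gingival bleeding, periodontal probing, and attachment loss will be monitored for each patient at every visit".

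**Outcome lists.** Study Design: "Primary outcome measures will include: presence of bleeding on probing, probing depth, and the progression of bone loss around the implant", and "Secondary outcome measures will include: Gingival index (GI), Plaque Index, mobility, and suppuration". The Scientific Abstract has a different primary list: "Primary outcome measures will be the presence of bleeding on probing, gingival index and the progression of bone loss around the implant". Attachment level and recession are in none of the three.

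**Sample size.** Statistical Procedures bases it on probing depth alone: a 1.72 mm difference at 9 months, SD 1.13 mm, 13 patients per arm.

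**The concern.** Probing depth runs from the soft-tissue margin to the base of the pocket. If the margin is cut down in one arm only and has not regrown by 9 months, that arm shows shallower pockets even if the attachment has not moved. Randomization and blinding do not remove this, because the mechanism is part of the assigned treatment.

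Attachment level and recession tell a lowered margin from a gain in attachment. Both are collected, but the plan commits to no analysis or report of either. A reader could then see a difference in the outcome that drives the sample size with no assurance of being able to tell which of the two it reflects.

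**Working it through.** **1. The plan's own figure.** Inputs from Statistical Procedures: difference 1.72 mm, SD 1.13 mm, power 90%, alpha 0.05 (taken as two-sided), 1:1.

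- Normal formula: n = 2(1.960 + 1.282)² × (1.13/1.72)² = 9.07, so 10 per arm.
- Two-sided t-test: 10.13, so 11 per arm.
- Power at the stated 13 per arm: 96.1% (t-test).

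The stated 13 is somewhat more than its inputs need. That is a separate and conservative discrepancy, and nothing below depends on it.

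**2. The mechanism.** With a fixed reference point, attachment level = probing depth + recession. If the margin drops by m mm and the pocket base stays put, probing depth changes by −m, recession by +m and attachment level by 0. If a share f of laser patients lose m mm net, the mean probing-depth shift is f × m.

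**3. Possible size.** The documents give neither f nor m, so both are assumed. Set-up: 13 per arm, one normally distributed value per patient, SD 1.13 mm, no attachment effect, pooled two-sided t-test at 0.05, counting only significant results that favour the laser; 400,000 simulated trials per cell. With f = 0 the chance is 2.5%.

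| Share f | Shift, m = 1 mm | Shift as share of 1.72 mm | Chance, m = 1 mm | Shift, m = 0.5 mm | Chance, m = 0.5 mm |
|---|---|---|---|---|---|
| 25% | 0.25 mm | 15% | 7.4% | 0.125 mm | 4.5% |
| 50% | 0.50 mm | 29% | 17.7% | 0.25 mm | 7.7% |
| 75% | 0.75 mm | 44% | 35.0% | 0.375 mm | 12.4% |
| 100% | 1.00 mm | 58% | 58.2% | 0.50 mm | 19.1% |

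The noncentral t-distribution gives 58.1% and 19.0% for the last row, in agreement.

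**4. Precision of attachment level at this sample size.** 95% CI half-width = t(24 df) × SD × √(2/13), with t = 2.064.

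- Probing depth: 2.064 × 1.13 × 0.392 = 0.91 mm.
- Attachment level, if recession adds an independent SD s (assumed): SD = √(1.13² + s²).
  - s = 0.5 mm: SD 1.24 mm, half-width 1.00 mm.
  - s = 1.0 mm: SD 1.51 mm, half-width 1.22 mm.

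**5. Baseline adjustment (a separate matter).** ANCOVA multiplies the variance by 1 − r², where r is the correlation of baseline with 9-month values (assumed). At r = 0.3 the factor is 0.91 and the probing-depth half-width 0.87 mm. At r = 0.6 they are 0.64 and 0.73 mm (23 df).

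**The case against.** The strongest reply is that nothing needed is missing. Attachment level and recession are scheduled in the same sentence as probing depth, for both arms and at both time points, and the Study Design lists are worded as inclusive, so reporting is not prevented. The lists are also a poor guide to what will be assessed: gingival index, plaque index, mobility and suppuration are listed there but are absent from the follow-up assessment sentence. This stands, and it is why the fix is cheap. It does not make the reporting pre-specified.

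Second, the trial compares the Repair Protocol as a package with conventional treatment, so a lower margin is part of a real effect, and no passage claims attachment gain. This also stands. The ambiguity concerns what the difference means, not whether the package comparison is valid. Attachment level would not establish decontamination as the cause either, because de-epithelialization, degranulation and bone decortication are likewise named only in the laser arm.

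Third, bleeding on probing and stent-standardized radiographic bone loss are co-listed primary measures that do not depend on the margin. They are a useful check but a partial one, since neither shows where the margin lies.

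Fourth, the size rests on assumptions. The 58% needs 1 mm of lasting loss in every laser patient, although gingivectomy is only as needed, and the manufacturer's instructions to which the plan defers may limit it. That is right: the table is a range, not an estimate.

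Fifth, the independent-SD assumption in step 4 may overstate the precision loss, because a lowered margin moves probing depth and recession in opposite directions. This is fair, and the 1.00 to 1.22 mm range should be read with that in mind.

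**Conclusion.** The concern holds. Gingivectomy is named for one arm only, probing depth depends on margin position, and the two measures that would resolve the ambiguity are collected without being listed as outcomes. A probing-depth difference could not by itself be read as attachment gain.

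The size cannot be derived from the documents: frequency, extent and regrowth are not given. Over the assumed range the chance of a significant result favouring the laser runs from about 5% to 58%, against 2.5% with no margin loss. The lower part is more plausible, because Study Procedures keeps the implants closed and Risks, Benefits, Alternatives describes the laser procedure as free of surgery. These probabilities are error rates only if the difference is read as attachment gain; for the package question they are power for a real effect.

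The closed-approach and surgery-free descriptions are also not reconciled with the gingivectomy step. The tension with the first is mild, since it excludes only incisions or flaps that uncover the implant surface; with the second it is plainer.

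This is a pilot and the comparison itself is not invalid, so the change should be made for clear interpretation. Confidence is medium because the size is unknown.

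**What to change.** - Name change in clinical attachment level from baseline to 9 months as a secondary outcome, and state its fixed reference point.
- Report recession beside probing depth, and interpret any probing-depth difference with both, using estimates and 95% CIs and no gatekeeping rule.
- State that a non-significant attachment-level result does not show absence of attachment gain at this sample size.
- Have the therapist record gingivectomy yes/no for each test implant, kept from the blinded examiners and used descriptively.
- Reconcile the closed-approach wording in Study Procedures and the surgery-free wording in Risks, Benefits, Alternatives with the gingivectomy step.

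Separately, and without bearing on gingivectomy: analyse probing depth and attachment level with one value per patient, by ANCOVA on the baseline value already collected.

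The cost is outcome-list and analysis wording plus one small data item, with no new visit or measurement. The downsides are a stricter reading of a positive probing-depth result and possibly a wider interval for attachment level than for probing depth.

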Dental implants are becoming more and more popular as a means to replace missing teeth. As more dental implants are being placed each year, clinicians are facing the challenges of common causes for failure or compromise of these dental implants. Gum disease, which has plagued natural teeth for many years, can manifest on dental implants in the form of a disease known as peri-implantitis. Peri-implantitis occurs when the presence of bacteria leads to inflammation of the area, and can be the reason for loss of bone around implants. Currently, there is no standard method for treating peri-implantitis. There are several common methods for treating this disease. One method involves cleaning off the implant with scalers in a manner similar to teeth during cleanings. The other method utilizes the same method and adds the use of a laser to remove most of the bacteria from the surface of the implant. In this study, we would like to compare these two methods and see if there is any additional benefit from using the laser technology. The goal is to determine which method is more effective at arresting the progression of peri-implantitis. For this means, we will be taking clinical measurements and X-rays. This will allow us to determine the status of the implant, improvement in the inflammation and changes in bone level. The implants will be treated at the baseline and checked during the follow-up appointments with the last appointment provided at the 9 months.

Risks, Benefits, Alternatives

The risk involved with the laser debridement directly to the patient is minimal. Potential risks may be postoperative infection or soft tissue trauma. The procedure is a conservative surgery-free debridement of the implant with the Biolase laser, and there is very little risk of having postoperative complications. Proper protocol for laser safety will be followed when utilizing the Biolase laser. Both procedures involved with the study are the standard of care for treatment.

Risks and complications of the use of lasers involve: eye and skin damage, thermal damage of the tissues and the adjacent structures, alterations of the implant, restorations of other surfaces, damage of critical structures (i.e. nerves and vessels), embolism, water splashing and rupture of the tip of the laser.

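### The risk text calls the laser treatment surgery-free and minimal-risk, yet the test-arm steps include gingivectomy and bone decortication, and the anticipated harms are not recorded by arm

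*Combined protocol and SAP*

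**What the plan says.** **Risk description (Risks, Benefits, Alternatives).** The section opens with "The risk involved with the laser debridement directly to the patient is minimal" and continues with "Potential risks may be postoperative infection or soft tissue trauma". It then says "The procedure is a conservative surgery-free debridement of the implant with the Biolase laser". A later paragraph of the same section lists further laser risks: eye and skin damage, thermal damage, alteration of the implant, injury to nerves and vessels, embolism, water splashing and tip rupture.

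**What is done (Study Procedures).** For both arms: "All ailing implants will be left closed with no incisions or flaps made to expose the implant surface surgically". The test arm then receives the Repair Protocol. Its step list is expressly open-ended and names "Outer Pocket De-Epithelialization, Gingivectomy (as needed), De-Epithelialization and Retraction, Scaling and Root planing, Sulcular Debridement/Degranulation, Bone Decortication", and after these a last round of sulcular debridement and compression. The control arm receives debridement with curettes and an ultrasonic scaler and, according to Study Design, a sham pass with the laser switched off. Both arms have occlusal adjustment.

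**Monitoring (Data and Safety Monitoring).** "There is minimal risk, and therefore there will be no data and safety monitoring board involved". The routine safety readings are gingival bleeding, probing and attachment loss. Investigators also look for unexpected outcomes after each visit and report patients with aberrant findings to the IRB.

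**Outcomes (Study Design).** Three primary and four secondary measures are listed. None is a safety outcome.

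**The concern.** The description on which the risk is rated is narrower than the treatment that is delivered. Debridement of an implant surface does not describe a procedure that may remove gingiva and that includes a bone step. Because the monitoring section draws its conclusion directly from the risk rating, the mismatch carries through to the stated monitoring rationale.

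The second consequence concerns what the trial can report. It names harms in advance and randomises patients between an active and a sham laser, so it could give a simple by-arm account of those harms. As written, it would finish without one.

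**Working it through.** No figure in the plan bears on this point, so the check is a comparison of the text, followed by two counts.

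**1. Does the risk text cover the listed steps?**
- Gingivectomy: in the test-arm list, qualified as needed. Not mentioned in the risk section.
- Bone decortication: in the test-arm list with no qualifier. Not mentioned in the risk section.
- The list is open-ended, so further unnamed steps are possible.
- The experimental-arm summary in Study Design and the account in the Lay Abstract do not mention either step.

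The firmer mismatch is therefore with decortication, because gingivectomy might not be performed in a given patient.

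**2. Can the passages be read together?**
- The closed-approach sentence in Study Procedures is limited by purpose: it rules out incisions or flaps made to reach the implant surface. The listed steps can be carried out within that limit, so there is no conflict inside Study Procedures.
- The surgery-free sentence in the risk section has no such limit. It neither says that it means flapless nor refers to the listed steps. This is where the conflict lies.

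**3. Does anything depend on it?**
- The monitoring section links minimal risk to the absence of a board with an explicit therefore. The stated reason thus rests on the risk description found incomplete in step 1.

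**4. Are the anticipated harms recorded by arm?**
- Outcomes in Study Design: 3 primary (bleeding on probing, probing depth, bone loss) + 4 secondary (gingival index, plaque index, mobility, suppuration) = 7. All are measures of the disease under treatment. Suppuration comes closest to a harm, but it is listed as a disease measure and not as postoperative infection.
- Routine readings in Data and Safety Monitoring: bleeding, probing, attachment loss. None is a harm named in the risk section.
- The check for unexpected outcomes is open-ended and could pick up a named harm. It is a patient-by-patient trigger for IRB reporting, its examples are again periodontal, and no by-arm record or summary is provided for.

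**5. How many patients?** Statistical Procedures gives 13 per arm, so 13 + 13 = 26. All 13 test patients are assigned a protocol that contains decortication. The number who would have gingivectomy cannot be derived from the documents.

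**The case against.** The strongest reply is that surgery-free simply means no open surgery. The protocol repeatedly calls the approach closed, and its background contrasts non-surgical therapy with resective or regenerative surgery. The plan also says that both procedures are standard of care and that patients would have needed the therapy anyway, so minimal risk may mean the risk added by the research. Both readings are plausible. But the risk section states neither, and its rating is applied to the laser debridement itself. What stands is that this may be loose wording and not a misjudged risk, and that rewording can cure it.

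Several stronger readings are tempting, and the documents do not support them:

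- **That the closed-approach sentence must change.** It is limited to exposure of the implant surface and is compatible with the listed steps.
- **That monitoring covers periodontal readings only, or is absent.** The check for unexpected outcomes is open-ended, aberrant findings go to the IRB, and all investigators share the task.
- **That a board is required.** Nothing here shows that a 26-patient pilot needs one; only the stated reason is in question.
- **That patients or the IRB were misinformed.** Consent pages are not in the available copy, the steps stand in the same IRB-approved protocol, and Recruitment provides for an interview on risks and for written consent.
- **That decortication is of a particular depth or technique.** The step is named but not described.
- **That bundling the steps spoils the comparison.** The declared purpose is to test the Repair Protocol as a package.
- **That a zero-event bound strengthens the case.** For 0 events in 13, the one-sided 95% upper limit is 1 − 0.05^(1/13) = 20.6%. It is the same with or without better recording, so it shows only that the trial is small.

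**Conclusion.** The point holds in a limited form. The unqualified surgery-free and minimal-risk description does not match a test-arm treatment that includes bone decortication and, where needed, gingivectomy. The stated reason for the monitoring arrangement inherits that mismatch. Separately, the plan provides no by-arm record of the harms that it anticipates itself.

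The effect is on the documented risk basis for 13 planned test patients and on the safety information obtainable from 26. It does not alter the efficacy analysis or the sample size, and no numerical size can be given for the risk. The conclusion assumes that the step list in Study Procedures describes what is done, and that no separate safety form exists outside the available documents. It is worth acting on because the remedy is cheap and the by-arm information would otherwise be lost.

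**What to change.** 1. Reconcile the risk wording in Risks, Benefits, Alternatives, and the minimal-risk basis in Data and Safety Monitoring, with the steps listed in Study Procedures. If surgery-free is meant as flapless, or minimal risk as risk added by the research, say so. Which steps belong in the treatment is for the investigators; this point takes no position on that.
2. Record for each test patient which Repair Protocol steps were performed. The therapist should hold this record, away from the blinded examiners.
3. Record the harms named in the risk section (infection, soft tissue trauma, thermal damage, nerve and vessel damage, embolism, tip rupture and the others listed) in both arms on one short checklist. Complete it at treatment and at the 1-week, 3-, 6- and 9-month visits, with an explicit entry for none. Enter it in the study file, since paper records are destroyed after transfer.
4. Add these harms to the outcome list as a descriptive safety outcome, reported as counts by arm without formal testing.

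The cost is a text amendment and a little extra form-filling at visits that already exist. No monitoring board, new visit or additional staff is needed.
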